16.1.1 Protocol

IGHID-12107 - The CM (HIV-CORE 008) Study Version 3.0
ChAdOx1.HIVcons62 (C62) boosted with MVA.tHIVcons4 (M4) or C62+
ChAdOx1.tHIVcons1 boosted with M4+MVA.tHIVcons3 (M3)

Confidential

Page 89 of 143

¹ Email the protocol team at [contact].

² Reference IGHID 12107 CQMP for additional details. Report according to FDA requirements for IND reporting: <https://www.fda.gov/drugs/investigational-new-drug-ind-application/ind-application-reporting-safety-reports>

9.1.1 Grade 1 and Grade 2 Toxicities

Participants who develop a Grade 1 or Grade 2 AE or regardless of relationship to study product may complete study treatment at the discretion of the site PI. Grade 1 or Grade 2 AEs that may be related to the vaccine/placebo injection will be handled according to standard clinical practice and documented. The adverse event will be monitored closely.

9.1.2 Grade 3 and Grade 4 Toxicities

For participants who develop a Grade 3 or Grade 4 AE following administration of vaccine/placebo, the site PI or designee must be notified within 24 hours. Grade 3 or Grade 4 AEs should be reported as described in [Table 21](#).

Grade 3 events

If a participant develops a Grade 3 AE, the participant may not receive further study product until:

- Written consultation and approval from the study PI (and SMC, as needed)
- The AE has returned to baseline or \leq Grade 2 and determined clinically stable by the site PI (or designee).

If any grade 3 AE has not returned to baseline or \leq Grade 2 within the D28 window, the vaccine can only proceed after consultation with the protocol team. Ideally, the booster vaccination is administered within 30 days of the Day 28 visit window but can be delayed up to 60 days after Day 28 visit window.

Grade 4 events

Grade 4 events at least possibly related to study treatment will result in permanent discontinuation of study product for the participant.

If a participant develops a Grade 4 AE not related to study treatment, the participant may not receive further study product until:

- Written consultation and approval from the study PI (and SMC, as needed)
- The AE has returned to baseline or \leq Grade 2 and determined clinically stable by the site PI (or designee).

Ideally, the booster vaccination is administered within 30 days of the Day 28 visit window but can be delayed up to 60 days after Day 28 visit window

9.2 AESI

9.2.1 **Potential blood clots AESIs and Thrombosis with Thrombocytopenia Syndrome (TTS)**

A high index of suspicion for blood clots should be maintained in participants who develop symptoms or diagnoses associated Thrombosis with Thrombocytopenia Syndrome (TTS), after receiving vaccine/placebo on study. The PI and study team must be notified immediately of all suspected cases. Signs and symptoms include: shortness of breath; chest pain; blurred vision or other vision changes; swelling, pain or erythema in a limb; severe or persistent abdominal pain; nausea or vomiting; dizziness; mental status changes; seizure, severe or persistent headache; easy bruising and/or bleeding; microhemorrhage beside the site of vaccination. If a participant experiences new onset (acute or subacute) symptoms listed above, there should be prompt evaluation, and consideration of prompt imaging to evaluate for the diagnoses listed below and hematology consultation. Associated diagnoses include:

- Deep vein thrombosis (DVT) – symptoms depend on location of thrombosis such as: swelling, pain, warmth of an extremity; headache, visual disturbances, seizures for sinus vein thrombosis; abdominal pain for intraabdominal thrombosis
- Pulmonary thromboembolism – sudden onset of shortness of breath, pleuritic chest pain, sudden death/pulseless electrical activity arrest
- Stroke or cerebral venous sinus thrombosis
- Myocardial infarction
- Arterial thrombosis

Initial evaluation should include the following:

- CBC with manual count
- D-dimer
- PT/INR
- PF4 antibody ELISA
- Fibrinogen

For any suspected TTS, WITHOLD further doses of vaccine/placebo until diagnostic evaluation has been completed and etiology of the signs and symptoms has been determined.

In cases of concern for TTS, see Appendix 5 for a recommended testing algorithm.

For this study, Vaccine-induced immune thrombotic thrombocytopenia (VITT) will be defined as the following:

- Platelet count $<150 \times 10^9/L$ with a confirmatory peripheral smear showing reduced platelets with no evidence of clumping (that could indicate falsely low platelet count)
- Presence of thrombosis/thromboembolism (refer to the list of MedDRA Preferred Terms proposed by the CDC; See Appendix 6) confirmed by:
 - 1) Imaging (i.e. ultrasound, CT scan, magnetic resonance imaging or venography or arteriography, echocardiogram, perfusion V/Q scan, conventional angiography, etc)
 - 2) Surgical Procedure (confirming presence of thrombus), i.e. thrombectomy

Pathologic examination, i.e. biopsy or autopsy

PFA antibody positive

Study staff will complete an AESI clotting form using the list of MedDRA Preferred Terms ([Appendix 6](#)) to ensure complete documentation of the event.

If evaluation provides evidence that TTS is unlikely, it is important to document the scientific evidence for and treat per standard clinical practice. Participants may continue study procedures unless clinically contraindicated.

If TTS is confirmed or probable, the participant should not receive additional vaccine/placebo, but should be followed for safety per the SOA and as clinically indicated. See Section [9.1](#) for expedited reporting as an AESI.

9.2.2 Potential Neurological AESIs

The PI and study team must be notified immediately of all suspected cases of neurological diseases. Neurological diseases are most commonly based on clinical symptoms.

If a participant experiences new onset (acute or subacute) motor or sensory disturbances (i.e., weakness, numbness, dysarthria, dysphagia, paresthesias, hypoesthesia, hyperesthesia, dysesthesias), bowel/bladder dysfunction, gait impairment, visual disturbance, or any event of myelitis, encephalomyelitis, transverse myelitis, or other sudden neurological deficit, there should be prompt neurological evaluation, including referral to a neurology specialist for further evaluation, testing and treatment, as clinically indicated. In cases of concern for spinal cord disease, see [Appendix 4](#) for a recommended testing algorithm which would be shared with providers caring for the participant.

For new onset neurological symptoms, proceed with the following:

- WITHHOLD further doses of vaccine/placebo until clinical and laboratory evaluation are completed and etiology of the symptoms or laboratory abnormalities are defined
- Consultation with neurology immediately

If neurological disease is confirmed or probable, the participant should not receive additional vaccine/placebo, but should be followed for safety per the SOA and as clinically indicated. See Section [9.5](#) for expedited reporting as an AESI.

9.2.3 *Delayed Dose*

In the event of acute illness or inability to return for Day 28, the booster vaccination can be delayed. The booster vaccine should ideally be given within 30 days after the Day 28 visit (booster vaccine dose) but can be extended up to 60 days, if needed. See Section [9.1.2](#) for additional instructions regarding delayed doses for Grade 3 or Grade 4 AEs.

9.2.4 *Consideration for SARS-CoV-2 Pandemic*

See [Appendix 3](#) for guidance about participant follow-up during periods of restrictions of in-person study visits due to local SARS-CoV-2 transmission. Participants should be tested for SARS-CoV-2 infection at the discretion of the site investigator according to any applicable local guidelines or SOC.

9.3 *Adverse Event Reporting*

The study will monitor participants for adverse events. Safety endpoints will include all adverse experiences, in addition to laboratory safety assessments, and vital signs. All AEs will be recorded on the appropriate study form.

AEs will be recorded in the database if any of the following criteria have been met:

1. Study treatment related Grade ≥ 1 AE
2. Grade ≥ 2 AEs
3. Autoimmune-related AEs regardless of grade
4. MAAEs regardless of grade
5. AESIs regardless of grade
6. HIV viral loads ≥ 50 copies/mL
7. Injection Reactions regardless of grade

8. AEs that led to a change in study treatment/intervention regardless of grade
9. AEs meeting SAE definition

9.3.1 *Local or Systemic Reactions to Vaccine/Placebo Injections*

9.3.1.1 *Grade 1 or 2*

Local reactions of Grade 1 or Grade 2 severity will usually resolve spontaneously. If needed, they may be managed with local application of cold packs, oral acetaminophen, oral non-steroidal anti-inflammatory agents, or a combination of these measures as appropriate.

NOTE: Topical steroids should not be applied to the injection site.

9.3.1.2 *Grade 3 or 4*

Grade 3 or Grade 4 local reactions ([Table 9](#) and [Table 11](#)) should be reported as described in [Table 21](#) (AESI per definition in Section 8.3.4). For Grade 4 local reactions, notify site PI or designee immediately (or Emergency response team, as appropriate) as definitive medical and/or surgical intervention should be undertaken as appropriate.

Grade 3 and Grade 4 systemic reactions ([Table 10](#) and [Table 12](#)) should be reported as described in [Table 21](#). The common systemic adverse events usually seen with ChAdV-vectored vaccines and MVA-vectored vaccines are listed in Section 2.3.2 ([Table 9](#), [Table 10](#), [Table 11](#), and [Table 12](#)). These events usually occur within 24 hours of vaccination and will resolve within the following 48 hours. It is anticipated that the majority of systemic adverse events post vaccination will be mild in intensity. However, there is a possibility of moderate or severe headache or malaise.

9.3.1.3 *Injection Site Reaction*

Injection Site Erythema or Redness and Injection Site Induration or Swelling will not be considered an AE if there is no interference with usual social and functional activities such that:

1. Grade 1: 2.5 to < 5 cm in diameter OR 6.25 to < 25 cm² surface area;
2. Grade 2: ≥ 5 to < 10 cm in diameter OR ≥ 25 to < 100 cm² surface area;
3. Grade 3: ≥ 10 cm in diameter OR ≥ 100 cm² surface area OR Ulceration OR Secondary infection OR Sterile abscess OR Drainage;
4. Grade 4: Potentially life-threatening consequences (e.g., abscess, exfoliative dermatitis, necrosis involving dermis or deeper tissue)

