8.2.9 Post Vaccination Symptom Diary

Solicited AEs will be captured in the post vaccination symptom diary given to each participant following each vaccination. Reference Table 9, Table 10, Table 11, and Table 12 for a complete list of the predefined solicited AEs for reactogenicity assessment.

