An AESI (serious or non-serious) is one of scientific and medical concern specific to the sponsor's product or program, for which ongoing monitoring and rapid communication by the investigator to the sponsor can be appropriate. Such an event might warrant further investigation in order to characterize and understand it. Depending on the nature of the event, rapid communication by the trial sponsor to other parties (e.g., regulators) might also be warranted.

AESIs will be collected according to the timepoints in the SoA (Section 1.3).

An AESI can be serious or non-serious. All AESIs will be recorded in the participant chart and the database.

Serious AESIs will be recorded and reported as per Section 9.5.

AESI for this protocol include those listed below.

1. Grade 3 or greater Injection Site Reactions
2. Immune-related AEs of any grade
3. Blood clot related events any grade (as per Section 9.2.1)
4. New onset neurological diseases of any grade (as per Section 9.2.2)

NOTE: Participants with an ongoing AESI at EOS should be followed until the AESI has resolved or stabilized in the opinion of the study team.

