9 CLINICAL MANAGEMENT

9.1 Toxicities

Adverse events will be graded according to the DAIDS AE Grading Table. The PI (or designee) is responsible for appropriate reporting of AEs to the regulatory authorities.

Table 21 Expedited Reporting Guidelines

Entity (Notification Method)	Protocol Team (Email ¹)	SMC (Email)	NIH DAIDS and DAIDS MO	University of Oxford (Email)	UNC IRB (PRI)	FDA ²
Personnel Responsible for Reporting	Site PI	Protocol PI	Site PI	Protocol PI	Protocol PI	Protocol PI
Grade 3 AEs (including local or systemic reactions)	Within 24 hours of site awareness (report again within 24 hours if AE does not return to ≤G2 after 14 days)	As determined per protocol team (report again within 24 hours if AE does not return to ≤G2 after 14 days)				
Grade 4 AEs (including local or systemic reactions)	Within 24 hours of site awareness (report again within 24 hours if AE does not return to ≤G2 after 14 days)	Within 24 hours of protocol team awareness (report again within 24 hours if AE does not return to ≤G2 after 14 days)	Within 3 days of site awareness	Within 3 days of site awareness	Report according to UNC IRB Promptly Reportable Information SOPs (SOPs 1401, 1402)	Report according to FDA requirements for IND reporting
Grade 3 or 4 allergic or hypersensitivity reactions at least possibly related to study treatment	Within 24 hours of site awareness	Within 24 hours of protocol team awareness	Within 3 days of site awareness	Within 3 days of site awareness	Report according to UNC IRB Promptly Reportable Information SOPs (SOPs 1401, 1402)	Report according to FDA requirements for IND reporting
AESIs	Within 24 hours of site awareness (AESI Clotting Form)	Within 24 hours of site awareness	Within 24 hours of site awareness	Within 3 days of site awareness	Report according to UNC IRB Promptly Reportable Information SOPs (SOPs 1401, 1402)	Report according to FDA requirements for IND reporting
SAEs NOT related to study treatment	Within 24 hours of site awareness	As determined per protocol team	Within 3 days of site awareness	Within 3 days of site awareness		Report according to FDA requirements for IND reporting

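### Read literally, Protocol 9.3.1.3 removes some related Grade 3 or higher injection-site reactions from the primary safety endpoint, contradicting the other passages that classify them

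*Protocol*

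**What the plan says.** Protocol 9.3.1.3 covers erythema or redness and induration or swelling at the injection site. It reads "Injection Site Induration or Swelling will not be considered an AE if there is no interference with usual social and functional activities such that", followed by four numbered items, Grade 1 to Grade 4. Grade 3 can be met by size alone (a diameter of 10 cm is enough) or by a lesion; the item ends "surface area OR Ulceration OR Secondary infection OR Sterile abscess OR Drainage". Interference with activities is not part of that grade.

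The primary safety endpoint (Protocol Table 13 and 10.2; SAP 6.2) is at least one Grade 3 or higher AE, possibly or definitely related, from Day 0 to 28 days after the boost. Its one stated exclusion (Table 13, 10.7.2, SAP 6.2) is a Grade 3 blood pressure rise during leukapheresis that resolves afterwards.

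Other passages classify the same reactions without an interference condition:

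- **8.2.9** points to Tables 9 to 12 for a "complete list of the predefined solicited AEs for reactogenicity assessment". Tables 9 and 11 name erythema and swelling; Table 11 adds induration.
- **8.3.4** lists "Grade 3 or greater Injection Site Reactions" among the AESIs, and **8.1.5.j** has solicited AEs that meet the AESI criteria reported as AESIs.
- **9.3 item 7**, in the list of AEs to be entered in the database, names "Injection Reactions regardless of grade".
- **9.3.1.2** sends Grade 3 or 4 local reactions to Table 21, with the gloss "AESI per definition in Section 8.3.4".
- **Table 21** has a row that begins "Grade 3 AEs (including local or systemic reactions".
- **SAP 6.2**, sixth planned table, presents AESIs as a category of AEs.

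**The concern.** The primary endpoint counts AEs, so a sentence that declares something not to be an AE works as an exclusion from the endpoint. This one is not stated where the endpoint is defined or analysed, and it runs against the passages above. The first criterion in 11.5.1 is written in terms of the primary safety outcome and inherits the same uncertainty. So does 9.1.2, whose Grade 3 provisions are triggered by an AE.

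With 8 participants per vaccine arm, the classification of one reaction changes the reported proportion and its confidence limit visibly. If the reading is chosen only after results by arm are known, the choice can no longer be shown to be independent of them.

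**Working it through.** **Step 1: follow one case under each reading.** Take a related erythema of 10 cm, Grade 3 by size, with no interference with activities.

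- Under 9.3.1.3 read literally: not an AE, so not a primary event and not counted in 11.5.1.
- Under the other passages: a solicited AE (8.2.9, Tables 9 and 11); an AESI because it is Grade 3 (8.3.4, 8.1.5.j, 9.3.1.2); reported through Table 21; tabulated among AEs (SAP 6.2, sixth table); hence a primary event because it is Grade 3 and related (10.2).

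The same reaction cannot be an adverse event of special interest and also not an adverse event.

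**Step 2: look for a repair.** The January 2024 clarification memo has five items: 4.1, 8.1.5.j, 8.4.2, 10.2 and Appendix 6. None touches 9.3.1.3. The change to 8.1.5.j concerns the period of assessment and leaves the AESI sentence as it was. For the secondary endpoint the notes in Protocol 10.7.3 and SAP 7.2 bring in reportable solicited AEs and AESIs, so the conflict there is weak. Protocol 10.7.2 and SAP 6.2 carry no matching note.

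**Step 3: reproduce the plan's limits.** Inputs are n = 8 per arm, n = 16 pooled, and exact one-sided 95% limits (Protocol 10.3, SAP 5.2). The upper limit U for x events in n solves P(X ≤ x | n, U) = 0.05.

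- 0/8: U = 1 − 0.05^(1/8) = 1 − 0.6877 = 0.312. Plan: 31%.
- 1/8: (1 − U)^8 + 8U(1 − U)^7 = 0.05 gives U = 0.471 (at U = 0.4707 the terms are 0.0062 + 0.0438 = 0.0500). Plan: 47%.
- 0/16: U = 1 − 0.05^(1/16) = 0.171. Plan: 17%.

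All three agree after rounding.

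**Step 4: effect of the reading,** if one such reaction is the only event.

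| | Not an AE | An AE |
|---|---|---|
| One arm | 0/8 = 0%, limit 31.2% | 1/8 = 12.5%, limit 47.1% |
| Both vaccine arms pooled | 0/16 = 0%, limit 17.1% | 1/16 = 6.25%, limit 26.4% |

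**Step 5: how often it could arise.** The documents give no rate. For assumed rates p per participant, the chance of at least one such reaction in an arm of 8 is 1 − (1 − p)^8: 0% at p = 0, 7.7% at 1%, 14.9% at 2% and 33.7% at 5%. These are assumptions to show the range, not estimates. The chance that the reaction is also the arm's only primary event cannot exceed these figures.

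**The case against.** The strongest reply is that the plan, read as a whole, already answers the question. Section 8.3.4 makes every Grade 3 or greater injection-site reaction an AESI, 8.1.5.j has it reported as one, the SAP's own primary section tabulates AESIs as AEs, and 9.3 states "Safety endpoints will include all adverse experiences". When the authors wanted a Grade 3 event left out of the endpoint, they said so, and only for blood pressure. The literal reading is also hard to believe: it would take potentially life-threatening Grade 4 reactions out of the AE definition directly after 9.3.1.2 asks for immediate notification of Grade 4 local reactions. Finally, 8.3 says solicited AEs are assessed separately from unsolicited ones, so the sentence may only mean that such a reaction is not entered again as an unsolicited AE.

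Most of this stands. A reader might infer that the plan has no rule for these reactions; that goes too far, because the passages together point towards counting them. What remains is that the one section devoted to injection-site reactions says the opposite and lists Grades 3 and 4 under that sentence. Nothing says which text prevails. The separate-entry reading is possible, mainly for lower grades, but 9.3.1.3 does not say it.

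**Conclusion.** The contradiction is real and narrow. It concerns classification: 9.3.1.3, taken literally, is an unstated exclusion from the primary endpoint. The size is conditional: 0/8 against 1/8, or an upper limit of 31.2% against 47.1%, if one related Grade 3 or higher reaction without interference is an arm's only event.

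Three stronger conclusions are tempting and are not supported.

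- **Lost safety data.** Injection reactions go into the database at any grade (9.3 item 7), and AESIs reach the SMC within 24 hours of site awareness (Table 21).
- **A biased primary result.** Nothing shows that such a reaction occurred or was left out.
- **A rate taken from the background tables.** In the earlier MVA study the 17 itemised Grade 3 events (1+1+1+2+3+3+3+3 in 2.3.2) include none that is local, and the COV002 rows of Table 4 report no severe local symptoms. This suggests a low frequency but gives no usable rate. Table 6 does not itemise every Grade 3 event, the Table 4 rows may include comparator recipients, and the vaccines and regimens differ.

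Severity is minor to should-fix: the consequence is small and uncertain, but it touches the primary endpoint and costs little to settle.

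**What to change.** Before arm-specific results are reviewed, which is when SAP section 9 wants decisions on planned analyses made as far as possible:

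1. Issue a clarification memo that reconciles 9.3.1.3 with 8.1.5.j, 8.2.9, 8.3.4, 9.3 item 7, 9.3.1.2 and Table 21. If the four items were meant as a grading scale, say so.
2. Add one line to Protocol 10.7.2 and to SAP 6.2: the primary endpoint classifies injection-site reactions consistently with 8.3.4, Table 21 and the AESI table in SAP 6.2, and the 9.3.1.3 sentence is not an exclusion.
3. If results by arm have already been seen and such an event occurred, report the primary proportion and its limit both ways.

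The sponsor must also reconcile 9.3.1.3 with 9.1.2 and 11.5.1. No clinical, dosing or pause rule is proposed here.

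The cost is a short memo and two one-line additions. No new data are needed, because the reactions are already recorded. If such a reaction occurred, the reported event rate may be slightly less favourable.

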9.3.2 Allergic or Hypersensitivity Reactions

Record all allergic and hypersensitivity reactions with both grade severity and attribution. Serious allergic or hypersensitivity reactions (\geq Grade 3) that are deemed possibly related to the study treatment by the PI (or designee) will be reported as described in [Table 21 and as detailed at https://www.fda.gov/drugs/investigational-new-drug-ind-application/ind-application-reporting-safety-reports](https://www.fda.gov/drugs/investigational-new-drug-ind-application/ind-application-reporting-safety-reports).

9.3.3 Monitoring HIV RNA levels

In the event of viremia of \geq 50 copies/mL the following should occur per standard of care:

- a. Adherence to ART should be carefully assessed and documented.
- b. A standard HIV RNA assay should be repeated within 1-4 weeks.
- c. HIV resistance testing will be performed at the time of drawing a confirmatory sample and as indicated for persistent viremia.
- d. For HIV RNA confirmed >200 copies/mL on repeat testing, stored samples may be tested for the presence of one or more ARV drugs in the participant's regimen.
- e. HIV RNA will be repeated every 2 weeks, or sooner as clinically indicated, until <50 copies/mL and the participant can continue on study.
- f. In the event of confirmed viremia and documented adherence to ART, ART should be managed by the primary care provider in discussion with the study team. The results of the HIV resistance tests will be shared with the participants and their care providers.

The protocol team will monitor the conduct and safety of the study via monthly meetings and regular summaries. Accrual, baseline characteristics, conduct of the study (including premature study discontinuations), any interruptions of ART, virologic failures, and all reported toxicities and events will be monitored during the study and discussed monthly with the protocol team or more frequently, if needed.

The protocol team will review the individual safety data monthly to assess relation of all reported toxicities and AEs to the study treatment. A study unique independent Safety Monitoring Committee (SMC) will receive quarterly study progress and safety monitoring reports. Study feasibility and the achievement of study milestones will be assessed in these reports. The DAIDS program and medical officers will review and assess the monthly safety reports, as well as SAE reports for potential impact on the study participant safety and protocol conduct as per DAIDS policies, guidance documents, and SOPs, as applicable.

